6.1 Visit 1, Screening Visit (-28 to -7 days)

A tabulated summary of all visits and assessments described in the following sections is provided in Table S-1, Schedule of Events. To the extent possible, subjects will be expected to adhere to the established visit schedule.

After discussing the study with the investigator/appropriate study staff and after agreeing to study participation by signing the consent, subjects will be assigned a subject number. For any subject, it is the responsibility of the investigator or study team member to obtain written informed consent (subject's signature) prior to performing any protocol-mandated assessment.

However, assessments performed as part of the routine care of the subject may be used to assess eligibility. The subject number will identify the subject throughout the study. In case of re-screening, the subject number assigned during the first screening procedure will be retained.

Patients meeting the entry criteria and consenting to participate in the protocol will undergo the following:

- Eligibility confirmation and informed consent discussion and documentation
- Review of medications
- Brief Physical examination
- Medical history
- Respiratory infection assessment
- Demographic Information
- Quality of Life (QoL) questionnaire
- Mini-Mental State Examination (MMSE) cognitive status assessment
- ECG – assessment of QTc interval
- Vital signs (orthostatic blood pressure, temperature, respiratory rate, height, weight, oxygen saturation and heart rate)
- Blood work – screening labs [serum chemistry, hematology, coagulation, CMV, serum virology, cytokines, study drug related antibodies, long interspersed nuclear elements-(LINE-1), peripheral blood mononuclear cells (PBMCs) and biomarkers of senescence]
- Urine collection for urinalysis
- Frailty Assessments (includes questionnaires, physical function testing and body composition)

6.2 Visit 2, Treatment Visit – Day 0

This visit will be recorded as "Day 0" and will require a visit to the research center where the following tests will be performed:

- Vital signs (orthostatic blood pressure, oxygen saturation, temperature, respiratory rate, weight, and heart rate) prior to vaccine and investigational product administration and 2, 4 and 6 hours post administration
- Review of medications
- Review of adverse events
- Respiratory infection assessment
- COVID-19 Screening questionnaire
- Flu vaccine administration
- Investigational product administration
- Nasal swab
- Blood work for pharmacodynamics, vaccine related antibodies, LINE-1, serum antibody testing, and peripheral blood mononuclear cells (PBMCs) prior to vaccine and investigational product administration and 2, 4 and 6 hours post administration
- SAVE procedures (if applicable)

After the observation period (6 hours) and prior to discharge from the Clinical Research and Trials Unit, a reassessment of vital signs including orthostatic blood pressures will be conducted on all study participants.

6.3 Visit 3, Safety Follow-up –Day 1

This visit will be recorded as “Day 1” and will require a visit to the research center where the following tests will be performed:

- Brief physical examination
- Vital signs (orthostatic blood pressure, oxygen saturation, temperature, respiratory rate, weight, and heart rate)
- Review of medications
- Review of adverse events
- Respiratory infection assessment
- Quality of Life (QoL) questionnaire
- ECG
- Blood work – labs [serum chemistry, Hematology, coagulation, cytokines, LINE-1, and vaccine related antibodies]
- Urine collection for urinalysis

6.4 Visit 4, Safety Follow-up –Day 7 (remote visit)

This visit will be recorded as “Day 7” and will be a remote visit where the following tests will be performed:

- Review of medications
- Review of adverse events
- Respiratory infection assessment
- Quality of Life (QoL) questionnaire

6.5 Visit 5, Follow-up - Month 1

This visit will be recorded as “Month 1” and will require a visit to the research center where the following tests will be performed:

- Vital signs (orthostatic blood pressure, oxygen saturation temperature, respiratory rate, weight, and heart rate)
- Review of medications
- Review of adverse events
- Respiratory infection assessment
- Quality of Life (QoL) questionnaire
- ECG
- Blood work – labs [serum chemistry, Hematology, coagulation, CMV, cytokines, vaccine related antibodies, LINE-1, peripheral blood mononuclear cells (PBMCs) and biomarkers of senescence]
- Urine collection for urinalysis

6.6 Visit 6, Follow-up – Month 2

This visit will be recorded as “Month 2” and will require a visit to the research center where the following tests will be performed:

- Vital signs (orthostatic blood pressure, oxygen saturation temperature, respiratory rate, weight, and heart rate)
- Review of medications
- Review of adverse events
- Respiratory infection assessment
- Quality of Life (QoL) questionnaire
- ECG
- Blood work – labs [serum chemistry, Hematology, coagulation, cytokines, vaccine related antibodies, LINE-1, and peripheral blood mononuclear cells (PBMCs)]
- Urine collection for urinalysis
- Frailty Assessments (includes questionnaires, physical function testing and body composition)

6.7 Visit 7, Follow-up – Month 6

This visit will be recorded as “Month 6” and will require a visit to the research center where the following tests will be performed:

- Vital signs (orthostatic blood pressure, oxygen saturation temperature, respiratory rate, weight, and heart rate)
- Review of medications
- Review of adverse events
- Respiratory infection assessment
- Quality of Life (QoL) questionnaire
- ECG
- Blood work – labs [serum chemistry, Hematology, coagulation, CMV, cytokines, LINE-1, and vaccine related antibodies]
- Urine collection for urinalysis
- Frailty Assessments (includes questionnaires, physical function testing and body composition)

6.8 Visit 8, Follow-up – Month 12

This visit will be recorded as “Month 12” and will require a visit to the research center where the following tests will be performed:

- Vital signs (orthostatic blood pressure, oxygen saturation, temperature, respiratory rate, weight, and heart rate)
- Review of medications
- Review of adverse events
- Respiratory infection assessment
- Quality of Life (QoL) questionnaire
- COVID-19 Screening questionnaire
- ECG
- Nasal Swab
- Blood work – labs [serum chemistry, Hematology, coagulation, cytokines, and vaccine related antibodies, LINE-1, peripheral blood mononuclear cells (PBMCs) and serum antibody testing]
- Urine collection for urinalysis
- Frailty Assessments (includes questionnaires, physical function testing and body composition)

6.9 Monthly phone visits – Month 3- Month 11

The following tests will be performed remotely (phone visits):

- Review of adverse events
- Review of medications
- Respiratory infection assessment
- COVID-19 Screening questionnaire

6.10 Examinations and Procedures

- Physical examinations will be limited to cardiac, pulmonary, abdominal, integumentary, and gross neurological evaluation, and to other systems based on specific subject complaints.
- Medical history is to be documented at Screening for each subject
- Vital signs, including pulse, orthostatic blood pressure, heart rate, respiratory rate, oxygen saturation and temperature will be measured.
- Height and weight will be obtained at the screening visit; weight will be obtained at each additional visit. Body mass index (BMI) will be recorded.
- A 12-lead electrocardiogram (ECG) will be performed. The Investigator will review and assess all abnormal results for clinical significance. Any post-baseline ECG abnormalities assessed as clinically significant will be recorded as AEs.
- Prior/Concomitant medications will be assessed at every site and remote visit.

6.11 Laboratory Assessments

The following laboratory assessments will be collected at the time points specified in the schedule of events. The Investigator will be provided all laboratory results and will review and assess out-of-range findings for clinical significance. Any post-baseline abnormal laboratory value assessed as clinically significant will be recorded as an AE.

Blood Tests:

- Serum Chemistry studies will include sodium, potassium, chloride, bicarbonate, BUN, creatinine, glucose, calcium, phosphorus, magnesium, total protein, albumin, ALT, AST, ALP, CK, LDH, GGT, total bilirubin, uric acid and CRP.
- Hematology parameters will include hematocrit, hemoglobin, erythrocyte count, absolute counts of leukocytes, neutrophils, lymphocytes, monocytes, eosinophils, basophils, platelet count.
- Coagulation studies will include PT and aPTT.
- Virology evaluation includes serum CMV, HIV antibody, HBsAg antibody, HBc antibody, HCV antibody, Subjects will a positive antibody evaluation for HBc or HCV should undergo evaluation for HBV DNA and for HCV RNA to determine if the antibody test may be falsely positive.
- PBMC Culture Supernatant Assessment will include 10 cytokine/chemokine mediators of adaptive immune function (IFN- γ , IL-1 β , IL-2, IL-4, IL-6, IL-8, IL-10, IL-12p70, IL-13 and TNF- α) test performed using Meso Scale Discovery, V-PLEX Proinflammatory panel human immunoassay kits.
- Serum for study related antibodies includes influenza antibody titers against A/H1N1, A/H3N2, and B viruses, LINE-1, and entolimod specific neutralizing antibodies.
- Plasma for cytokines will include G-CSF and IL-6 tests will be performed using the MSD assay platform as well as senescence biomarkers. These samples will be de-identified and shipped to the sponsor, GPI, in a coded format. Samples will be used for research purposes only as described in this protocol. The data will be reported to the Mayo Clinic team for the analysis. When the study is completed, the sponsor will destroy any remaining samples.
- COVID-19 testing will include COVID-19, PCR [SARS Coronavirus 2, Molecular Detection, PCR (NP)] and SARS-CoV-2 IgG Ab [SARS Coronavirus 2 IgG Ab, Serum]

Urine Tests:

- Urinalysis will include specific gravity, pH, protein, glucose, ketones, bilirubin, urobilinogen, blood, nitrate, leukocyte esterase as assessed by dipstick and microscopic urinalysis evaluating white blood cells, epithelial cell, bacteria, casts, and crystals.
- Urine will also be assessed for senescence biomarkers.

6.12 MMSE and Quality of Life (QoL) Assessments

The Mini-Mental State Examination (MMSE) is a 30-point questionnaire that is used to measure cognitive impairment. It includes tests of orientation, attention, memory, language and visual-spatial skills.

The Short Form (36) Health Survey will be administered to subjects. This survey consists of 36 questions and eight scaled scores (vitality, physical functioning, bodily pain, general health perceptions, physical role functioning, emotional role functioning, social role functioning, and mental health).

6.13 Frailty Assessments

Frailty phenotyping will consist of 5 measures, including grip strength, walking speed, body composition, and questionnaires that will assess endurance and energy, unintended weight loss and physical activity level.

Skin advanced glycation end products (AGEs) will be assayed using an *AGE Reader*[®]. This non-invasive method has a light source that illuminates a skin surface of approximately 4 cm² on the volar side of the forearm. The device uses an excitation light source with peak intensity of approximately 370 nm to excite fluorescent moieties in the tissue (skin autofluorescence), which then will emit light of a different wavelength. In the used wavelength band, the major contribution to fluorescence comes from fluorescent AGEs linked mostly to collagen. Emission light and reflected excitation light from the skin is measured with a spectrometer in the 300–600 nm range.

6.14 SAVE Assessments

SAVE is a non-invasive imaging technique used to measure viscoelastic characteristics of tissue. This technique enables imaging biphasic characteristics of tissue which are related to both extracellular matrix changes as well as disruption in the interstitial fluid mobility due to structural changes.

6.15 Adverse Events

Adverse event monitoring will be conducted throughout the study for all subjects. The AE and serious adverse event (SAE) reporting period begins at the time of informed consent and continues through study completion. Adverse events will be assessed at every site and remote visit.

The Investigator will follow-up on all AEs observed or reported by the subject up to the end of the reporting period or until follow-up is no longer necessary. The Investigator will follow-up on SAEs until they are considered resolved or the outcome is known.

Definitions, documentation, and reporting of AEs are described in Section 8. Serious adverse events must be reported within 24 hours as described in Section 8.2.

Table S-1. Schedule of Events

PERIOD	Screening Visit	Treatment Visit	Safety Follow-Up		Monthly Follow-Up					
ON-SITE VISIT	1	2	3	4 (remote)	5	6	-	7	-	8
WEEK	-4	0	Day 1	1						
MONTH					1	2	3 to 5 ^[p]	6	7 to 11 ^[p]	12
Visit Window, week(s)	-28 days			± 1 day	± 1 week					
General Eligibility, Safety, and Frailty Assessments										
Eligibility assessment	X									
Written informed consent	X									
MMSE cognitive status assessment	X									
Frailty assessments ^[a]	X						X	X		X
Brief physical examination ^[b]	X		X							
Medical history	X									
Demographic Information	X									
Vital signs/oxygen saturation/Ht/Wt ^[c]	X ^[q]	X ^{[d][q]}	X ^[q]		X ^[q]	X ^[q]		X ^[q]		X ^[q]
12-lead ECG	X		X		X	X		X		X
AE assessment, including respiratory infection assessment	X	X	X	X	X	X	X	X	X	X
Concomitant medications	X	X	X	X	X	X	X	X	X	X
Quality of life (QoL) questionnaire	X		X	X	X	X	X	X	X	X
Study Drug Administration										
Study drug		X								
Laboratory Assessments										
Serum chemistry ^[e]	X		X		X	X		X		X
Hematology ^[f]	X		X		X	X		X		X
Coagulation ^[g]	X		X		X	X		X		X
Serum virology ^[h]	X									
Urinalysis ^[i]	X		X		X	X		X		X
Serum for entolimod-reactive antibodies ^[j]	X		X		X	X		X		X
Plasma for pharmacodynamics ^[k]		X								
Serum for vaccine related antibodies ^[l]		X			X	X		X		X
Peripheral blood mononuclear cells (PBMC) ^[m]		X			X	X				X
COVID-19, PCR [SARS Coronavirus 2, Molecular Detection, PCR (NP)]		X								X
Exploratory Procedures										
SAVE ^[n]		X								
Biomarkers of senescence ^[o]		X			X			X		X
SARS-CoV-2 IgG Ab [SARS Coronavirus 2 IgG Ab, Serum]		X								X

Footnotes
[a] To be collected at screening, baseline, months 2, 6 and 12 (includes questionnaires, physical function testing, and body composition)
[b] Physical examination will be limited to cardiac, pulmonary, abdominal, integumentary, and gross neurological evaluation, and to other systems based on specific subject complaints.
[c] Height will only be collected at screening; weight will be collected at all in-person visits
[d] To be collected pre-treatment and 2, 4 and 6 hours post treatment. Wt will only be performed prior to study drug administration.
[e] Serum chemistry studies will include sodium, potassium, chloride, bicarbonate, BUN, creatinine, glucose, calcium, phosphorus, magnesium, total protein, albumin, ALT, AST, ALP, CK, LDH, GGT, total bilirubin, uric acid, and CRP.
[f] Hematology parameters will include hematocrit, hemoglobin, erythrocyte count; absolute counts of leukocytes, neutrophils, lymphocytes, monocytes, eosinophils, basophils; platelet count.
[g] Coagulation studies will include PT and aPTT.
[h] Virology evaluation includes serum CMV, HIV antibody, HBsAg antibody, HBC antibody, HCV antibody. Subjects with a positive antibody evaluation for HBC or HCV should undergo evaluation for HBV DNA and for HCV RNA to determine if the antibody test may be falsely positive. Only CMV testing will be carried out on months 1 and 2.
[i] Urinalysis will include specific gravity, pH, protein, glucose, ketones, bilirubin, urobilinogen, blood, nitrite, leukocyte esterase as assessed by dipstick and microscopic urinalysis evaluating white blood cells, red blood cells, epithelial cells, bacteria, casts, and crystals.
[j] Test will be performed by GPI. Samples may also be used for additional testing related to the study objectives.
[k] G-CSF and IL-6 tests will be performed using the MSD assay platform. Samples are to be collected pre-treatment and 2, 4 and 6 hours post treatment.
[l] Influenza antibody titers A/H1N1, A/H3N2, and B assessed by HAI Assay
[m] Meso Scale Discovery, V-PLEX Proinflammatory panel for 10 cytokine/chemokine mediators of adaptive immune function (IFN- γ , IL-1 β , IL-2, IL-4, IL-6, IL-8, IL-10, IL-12p70, IL-13 and TNF- α) and Interferon gamma ELISPOT assay
[n] Sub-hertz Analysis of ViscoElasticity (SAVE) will be performed 6 hours after study drug administration (or placebo) on left and right deltoid muscles in cohorts receiving entolimod (3 μ g and 10 μ g) and representing a total of 50 subjects.
[o] Blood and urine will be collected for analyses of senescence
[p] Subjects will be contacted bi-weekly via the telephone for remote follow-up visits
[q] Orthostatic blood pressures will be performed at all visits

Abbreviations: AE=adverse event, ALP=alkaline phosphatase, ALT=alanine aminotransferase, aPTT=activated partial thromboplastin time, AST=aspartate aminotransferase, BUN=blood urea nitrogen, CK=creatine kinase, CMV = cytomegalovirus, CRP=C-reactive protein, CTCAE=Common Terminology Criteria for Adverse Events, DNA=deoxyribonucleic acid, ECG=electrocardiogram, GGT=gamma-glutamyl transferase, HBC antibody=anti-hepatitis B core antibody, HBsAg=hepatitis B surface antigen, HBV=hepatitis B virus, HCV=hepatitis C virus, HIV=human immunodeficiency virus, IV=intravenous, LDH=lactate dehydrogenase, PT=partial thromboplastin time, RNA=ribonucleic acid, SARS-CoV-2 IgG Ab = severe acute respiratory syndrome coronavirus 2 immunoglobulin G antibody; SAVE= Sub-hertz Analysis of ViscoElasticity, USP=United States Pharmacopeia, PBMC=peripheral blood mononuclear cells

Supportive Care

General Recommendations

Consistent with subject safety and comfort, administration of any prescription or over-the-counter drug products other than study medication will be minimized during the study period, except those currently used for chronic medical conditions at the time of enrollment or those prescribed by the subject's physician if not specifically contraindicated by the study design. Subjects will be discouraged from use of herbal remedies, self-prescribed drugs, tobacco products, alcohol, marijuana, or street drugs during their participation in the clinical study.

If considered necessary for the subject's well-being, drugs for concomitant medical conditions or for symptom management may be given at the discretion of the investigator. The investigator's decision to authorize the use of any drug other than study drug will take into account subject safety, the medical need, the potential for drug interactions, the possibility for masking symptoms of a more significant underlying event, and whether use of the drug will compromise the outcome or integrity of the study.

Subjects will be instructed about the importance of the need to inform the clinic staff of the use of any drugs or remedies (whether prescribed, over-the-counter, or illicit) before and during the course of the study.

Recommendations with regard to specific types of concomitant therapies, supportive care, diet and other interventions are provided in the protocol. To minimize variations in supportive care, the recommended supportive care agents (e.g., loperamide, granisetron) should be used unless there is a medical rationale in a specific subject for use of an alternative product.

Anti-inflammatory or Antipyretic Drugs or Corticosteroids

Anti-inflammatory or antipyretic drugs may not be administered prophylactically. Thereafter, subjects may receive ibuprofen, 400 mg orally, as needed every 4 to 6 hours in response to constitutional symptoms, fever or malaise occurring following study drug administration. Other nonsteroidal anti-inflammatory drugs (NSAIDs) may be substituted as medically necessary. Post-entolimod use of acetaminophen, 650 mg orally as needed every 4 to 6 hours, may be used in response to constitutional or pyretic symptoms if medically necessary, but use of acetaminophen is not encouraged given its potential for adverse hepatic effects.

The use of systemic, topical, inhaled, or enteric corticosteroids during screening or on Day 1 should be avoided given that such drugs may confound interpretation of safety and pharmacodynamic responses in subjects on this study. However, such drugs are permitted after study drug administration if a subject develops an intercurrent condition that require corticosteroid therapy.

Support for Hypotension

In the event that a subject experiences hypotension (SBP <90 mm Hg or DBP <60 mm Hg; a > 20 mm Hg drop in SBP or > 10 mm Hg drop in SBP with symptoms at any time after administration of study drug or with orthostatics) it may be managed according to standards of

care until the SBP is ≥ 90 mmHg and the DBP is ≥ 60 mmHg on ≥ 2 determinations obtained ≥ 1 hour apart [or until BP approaches within 10% of baseline (pre-study drug values) with resolution of symptoms]. It should be emphasized that a subject's clinical condition, rather than blood pressure alone, should be the primary basis for any intervention or medical decision-making.

- As much as possible, subjects should be kept at rest following study drug administration.
- A subject requiring use of the bathroom should be evaluated for orthostatic changes. If the blood pressure is stable upon standing, and if the subject has no symptoms, the subject may ambulate to the bathroom, but study personnel should ensure the subject's safety. If there is a clinically significant drop in systolic blood pressure, or the subject complains of lightheadedness upon standing, the subject should be encouraged to use an emesis basin, urinal, bedpan, or bedside commode, as appropriate for the circumstances.
- For any hypotension more significant than minor dizziness, treatment should follow standard clinic protocol.

7 Statistical Plan

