3.6 Exploratory Endpoints

Sub-hertz Analysis of ViscoElasticity (SAVE) in muscle tissue in response to local immunological reactions due to influenza vaccination

SAVE is a non-invasive imaging technique used to measure viscoelastic characteristics of tissue. This technique enables imaging biphasic characteristics of tissue which are related to both extracellular matrix changes as well as disruption in the interstitial fluid mobility due to structural changes. A clinical study of this method in breast tumors has shown to provide effective separation of the benign from malignant breast lesions in patients [25].

In this study, SAVE will be used for quantification of muscle reaction in response to vaccination, which usually occurs within few hours of injection. Vaccine potency and efficiency are estimated by antigen-specific antibody titers and T-cell responses generated weeks after vaccination. Skeletal muscle contains few immune cells, but tissue resident and/or infiltrating immune cells encounter vaccine antigens for the first time at the site of administration. Thus, the magnitude of local innate immune responses starting at the vaccine delivery site (local inflammation) initially controls subsequent adaptive immune responses and may be captured by SAVE.

- Comparison of SAVE between left versus right deltoid muscles of the same individual.

Markers of Cell Senescence

- Changes in markers of senescence in blood and urine.

Efficacy

- Reduction of COVID-19 morbidity (detection of viral infection by PCR)

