5.2 Treatment Regimen

A single IM injection of study drug (entolimod or placebo) will be administered to each subject on the morning of vaccination, Day 1 (to be administered within 1 inch and within 1 minute of flu vaccine). The appropriate amount of study drug will be aseptically withdrawn from the required number of study drug vials into a 1-mL tuberculin syringe calibrated in 10-µL units. The drug will be administered from the syringe through a 22-25-gauge needle (see table 1 below) at a 90°-angle to the skin surface into the deltoid muscle between the acromion process and the midaxillary line.

Table 1. Needle size.

Female or Male up to 69 kg	22-25 gauge, 1 inch needle
Female 70 kg to 91 kg, Male 70 kg to 118 kg	22-25 gauge, 1 inch to 1.5 in needle
Female > 91 kg, Male > 118 kg	22-25 gauge, 1.5 inch needle

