5.3 Method for Assigning Subjects to Treatment Groups

Study subjects will be randomized in a dose-escalated 4-arm study of entolimod in 3 possible doses or placebo (see table 2 below). Beginning in period 1, the first eight patients in the 1ug arm will be evaluated for safety and tolerability by the DSMB prior to the enrollment of the remainder of the 1ug arm. In addition, after review we will proceed with recruitment in period 2 of the 3ug arm. Again, safety and tolerability will be assessed in the first 8 patients of the 3ug arm during period 2. Similarly, after evaluation by the DSMB we will proceed with the remainder of the 3ug arm. In period 3 we will evaluate safety and tolerability in the first 8 subjects of the 10ug arm. An evaluation by the DSMB will be completed and we will proceed with the remainder of the 10ug arm until all subjects have been accrued. We will recruit the balance of the subjects remaining to be enrolled (to obtain 25 subjects per arm) pending safety review by the DSMB.

Randomization will be performed using Medidata Balance software, integrated into the electronic case report forms Medidata RAVE. A permuted block design will be used, with stratification by sex. Subjects and study center personnel involved in the care of subjects will be blinded to study drug assignment (entolimod vs. placebo).

Table 2. Dose-Escalated 4-arm Study

Arm	Placebo	1ug	3ug	10ug
Period 1	2	6		
Period 2	2		6	
Period 3	2			6

Dose Levels

Cohorts of subjects will be sequentially enrolled at progressively higher starting dose levels. The following dose levels are planned:

- Dose Level 1: 1 μ g
- Dose Level 2: 3 μ g
- Dose Level 3: 10 μ g

These doses are within the dose range of 1 μ g to 10 μ g and equal or greater than five times less than that which has been previously evaluated in healthy subjects and patients with advanced solid tumors.

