5.8 Masking/Blinding of Study

In order to minimize the study bias, this study will use a process for randomized assignment to entolimod or placebo. The investigational drug blind will be maintained using the Research Pharmacy processes for preparation of the investigational product. All subjects and study personnel except for those directly involved with study drug preparation will be blinded to study

drug assignment for the entire study. All unblinded dosing information must be maintained in a secured area, accessible only by unblinded personnel.

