7.1 Sample Size Determination

A sample size of 25 per arm provides 90% power to detect a doubling (100% increase) in geometric mean influenza antibody titer A/H1N1 based on a one-sided two-sample t-test at alpha level 0.15. This calculation assumes a coefficient of variation of 2.0 for A/H1N1. Under the assumption of smaller coefficient of variation for A/H3N2 and B antibody titers of 1.4, 25 per arm provides 90% power to detect an 80% increase in these antibody titers at alpha level 0.15. Thus, we plan to enroll 25 to each arm, for a total sample size of 100. We anticipate greater power under the ANCOVA approach, adjusted for baseline levels of the titer.

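### The SAVE footnote contradicts itself on scanning placebo recipients, and the reading that fits its count of 50 would reveal active drug and leave no placebo comparator

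*Combined protocol and SAP*

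**What the plan says.** Table S-1 footnote [n] (section 6.15) schedules SAVE "6 hours after study drug administration (or placebo) on left and right deltoid muscles in cohorts receiving entolimod", names the 3 and 10 µg doses, and closes with "and representing a total of 50 subjects". The parenthesis implies that placebo recipients are scanned. The phrase "on left and right deltoid muscles in cohorts receiving entolimod", the named doses and the total point to the two higher-dose arms only.

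Other sections do not settle the matter:

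- Section 6.2 lists SAVE at the treatment visit as a conditional procedure and does not state the condition. Section 6.14 describes the technique but not who undergoes it.
- Section 3.6 lists SAVE as exploratory, aimed at the muscle's reaction to vaccination, with the endpoint "Comparison of SAVE between left versus right deltoid muscles of the same individual".
- Section 2 makes entolimod's effect on tissue viscoelasticity at the injection site part of a secondary, pharmacodynamic objective.
- Section 5.2 requires the study drug "to be administered within 1 inch and within 1 minute of flu vaccine".
- Section 5.8 states: "All subjects and study personnel except for those directly involved with study drug preparation will be blinded to study" drug assignment throughout the study.
- Section 7.2 does not name SAVE. It compares pharmacodynamic parameters across all four groups.

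**The concern.** A procedure done visibly in some subjects and not in others, selected by treatment, tells subjects and staff something about treatment. Here that would happen 6 hours after dosing, before all post-discharge follow-up. Adverse events are a primary endpoint. Their relatedness is judged by the sponsor-investigator (section 8.2.1), dose-limiting toxicity rests on investigator judgement (section 1.6.1), and two events judged at least possibly related in an arm trigger unblinding of the arms to an independent monitor (section 8.4). Respiratory infections are self-reported and quality of life is a questionnaire. All of these can shift with knowledge of allocation.

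The second issue is attribution. Vaccine and study drug go into the same muscle, so the injected-versus-opposite-arm difference is the reaction to both together. Without subjects who received vaccine plus placebo, the part due to entolimod cannot be separated.

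**Working it through.** **Inputs.** Section 5.3 plans "to obtain 25 subjects per arm". Section 7.1 says "we plan to enroll 25 to each arm, for a total sample size of 100". The four arms are placebo, 1, 3 and 10 µg. Before any scan, the chance of active drug is 75/100 = 75% and of placebo 25/100 = 25%. Table 2 (section 5.3) has three periods, each with 2 placebo and 6 active subjects.

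**Which head-count gives 50, and what scanning would reveal.**

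| Who is scanned | Number | Equals 50? | Active, if scanned | Placebo, if not scanned |
|---|---|---|---|---|
| A. 3 and 10 µg arms | 25 + 25 = 50 | yes | 50/50 = 100% | 25/50 = 50% |
| B. A plus all placebo | 50 + 25 = 75 | no | 50/75 = 67% | 0/25 = 0% |
| C. A plus placebo shared evenly over three dose cohorts | 2 × (25 + 25/3) = 66.7 | no | 50/66.7 = 75% | 8.3/33.3 = 25% |
| D. Table 2 subjects, periods 2 and 3 | 8 + 8 = 16 | no | 12/16 = 75% | 21/84 = 25% |
| E. 50 taken from C at 3:1 | 37.5 active + 12.5 placebo | by construction | 37.5/50 = 75% | 12.5/50 = 25% |

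Reading A reproduces the plan's figure directly. It is also the reading under which being scanned identifies active drug. Reading B moves the disclosure to the unscanned: they are exactly the 1 µg arm, so not being scanned means active drug. C, D and E are neutral between active and placebo.

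**Can C or E be carried out as the plan stands?** Both need every placebo subject to belong to a dose cohort. Table 2 defines such cohorts for 3 × 8 = 24 subjects; for the other 100 − 24 = 76 no rule says which placebo subjects belong with which dose. Section 3 restarts the 1 µg arm when the 3 µg arm opens, restarts the 3 µg arm when the 10 µg arm opens, and then continues all three together. In those stretches, someone who leaves out a 1 µg recipient has to know that recipient's arm. Section 5.8 limits that knowledge to those preparing the drug. Reading D avoids this only if confined to subjects known to be outside the 1 µg arm, and it gives 16 scans.

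**What the left-right difference estimates.** Write V for the local reaction to vaccine and E for any added reaction to entolimod. In an entolimod recipient, injected minus contralateral estimates V + E. In a placebo recipient it estimates V, with any reaction to the placebo injection. Isolating E needs the second group. Comparing 3 with 10 µg gives E at one dose minus E at the other: a dose difference, not an effect against placebo.

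**The case against.** The strongest reply is that the footnote itself mentions placebo, and that a cohort in this protocol can include placebo recipients. Section 5.3 speaks of eight patients in a dose arm, while Table 2 makes those eight 6 active and 2 placebo. On that view scanning follows the enrolment cohort, 50 is a target, and reading E applies: nothing about active versus placebo is revealed and placebo scans exist. Section 6.2 does not say that the condition for scanning is allocation. The left-right endpoint in section 3.6, aimed at the reaction to vaccination, uses the opposite arm as its own control and can be computed without placebo subjects.

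Much of this stands. A reader might infer that the plan definitely restricts scanning to 3 and 10 µg recipients, that half the trial will be known to be on active drug, and that SAVE can answer nothing. The documents do not support that: the placebo wording contradicts the restriction, and the section 3.6 endpoint survives.

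The cohort reading still does not rescue the plan. It would work if a dose cohort were assigned openly first and active or placebo blindly within it. Beyond Table 2 no such two-step assignment is described; section 3.2 has 100 subjects randomised to one of four groups. No stated rule both yields 50 and protects the blind.

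**Conclusion.** The point holds as an internal contradiction with consequences. Footnote [n] does not settle whether placebo recipients are scanned. On the reading that matches its count, scanning is selected by allocation. The chance of active drug goes from 75% to 100% in the 50 scanned subjects, and the chance of placebo from 25% to 50% in the 50 unscanned. The section 2 viscoelasticity objective then has no placebo comparator, and the four-group pharmacodynamic comparison in section 7.2 could not be made for SAVE.

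These figures assume full arms of 25 and that subjects or staff know, or work out, the selection rule. The exposure is to reported adverse events, relatedness, self-reported infections and quality of life after the 6-hour scan. The HAI titre is a laboratory measure and is little exposed. SAVE is exploratory in section 3.6, so the blind is the main reason to act.

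**What to change.** Reconcile footnote [n] with sections 2, 3.6, 5.8 and 6.2. State who is scanned, and select about 50 subjects by a rule that does not use assignment and that includes placebo. Two options:

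- A separate 1:1 scan or no-scan randomisation of all subjects, generated by the randomisation system.
- Scanning everyone enrolled in stated calendar periods in which placebo subjects are also being randomised.

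Replace the open condition in section 6.2 with that rule. Name the analysis in section 7.2: the injected-minus-contralateral difference per subject, each scanned entolimod arm against placebo. Also settle whether SAVE serves a secondary objective (section 2) or an exploratory endpoint (section 3.6).

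The cost is wording, with the number of scans roughly unchanged. A 1:1 selection gives 25/2 = 12.5 scans per arm on average, so about 12 to 13 instead of 25 at the two higher doses. The standard error of an arm mean there rises by a factor of √(25/12.5) = 1.41. In return, the placebo arm and the 1 µg arm each gain about 12 to 13 scans.
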